## Division & Personnel

### Division

What Division/Department does the PI belong to?  
Neurobiology and Therapeutics of Aging  
Within the division/department, what Center or group are you affiliated with, if any?  
Neurobiology and Therapeutics of Aging

## Procedures

To create the protocol summary form, first indicate if this research will include any of the following procedures

- ✓ Psychiatric Assessment
- ✓ Neuropsychological Evaluation
- ✓ Collection of Biological Specimens
- ✓ Medication Trial
- ✓ Use of Placebo or Sham Treatment
- ✓ PET/SPECT Scan
- ✓ MRI
- ✓ Off-label Use of Drug or Device

## Population

Indicate which of the following populations will be included in this research

- ✓ Adults over 50

## Research Support/Funding

Will an existing internal account be used to support the project?

No

Is the project externally funded or is external funding planned?

Yes

Select the number of external sources of funding that will be applicable to this study

## Funding Source #1

Is the PI of the grant/contract the same as the PI of the IRB protocol?

Yes

Select one of the following

The grant/contract is currently funded

Source of Funding

Federal

Institute/Agency

NIMH

Grant Name

Targeting Dopaminergic Mechanisms of Slowing to Improve Late Life Depression

Grant Number

R61 MH110029

Select one of the following

Single Site

Business Office

RFMH

Does the grant/contract involve a subcontract?

Yes

Subcontracted?

To

Name institution(s)

Columbia University

Stony Brook University

## Study Location

Indicate if the research is/will be conducted at any of the following

NYSPI

This protocol describes research conducted by the PI at other facilities/locations

No

## Lay Summary of Proposed Research

Lay Summary of Proposed Research

Individuals with Late Life Depression (LLD) often have cognitive problems, particularly problems with memory, attention, and problem solving, all of which contribute to antidepressant non-response. Our group and others have shown that decreased thinking speed is the central cause of functional problems in patients with LLD. Similarly, decreased walking speed is associated with depression and carries additional risk for falls, hospitalization, and death. Available evidence suggests that declining functionality in the brain's dopamine system contributes to age-related cognitive and motor slowing. The central hypothesis of this R61/R33 Phased Innovation Award is that by enhancing dopamine functioning in the brain and improving cognitive and motor slowing, administration of carbidopa/levodopa (L-DOPA) will improve depressive symptoms in older adults.

This IRB protocol pertains to the R33 Phase of this grant proposal (R61 Phase was approved under IRB #7270). In the R33 Phase 90 adults aged > 60 years with (1) a DSM 5 depressive disorder, (2) significant depressive symptoms, and (3) decreased thinking or walking speed will receive 8 weeks of treatment with

L-DOPA up to 450mg. We will test whether L-DOPA increases brain dopamine release using neuroimaging and whether it speeds up thinking and walking speed. Data collected in the proposed studies may help identify a new treatment for LLD, which could have large public health ramifications given the prevalence, frequent treatment resistance, and chronicity characteristic of LLD. This project also will elucidate the neurobiology of slowing at molecular, structural, and functional levels of analysis, increasing our understanding of the interplay between these aging-associated processes and the pathophysiologic changes underlying late life neuropsychiatric disorders. Exploring patient characteristics that predict response to L-DOPA may provide useful information to guide differential therapeutics and develop personalized medicine for LLD.

## Background, Significance and Rationale

### Background, Significance and Rationale

LLD affects 3% of community-dwelling adults over 60 years old (1), and 15% of older adults have clinically significant depressive symptoms (2). LLD increases an older adult's risk of disability by 67-73% over 6 year follow up (26), causes twice the functional impairment compared to those without LLD (27), increases mortality in patients with heart disease, and is associated with high rates of completed suicide in individuals over 65 (28-29). LLD is highly recurrent, can become chronic (30), and is often difficult to treat (31).

Executive Dysfunction (ED) is common in patients with LLD, predicts poorer acute response to antidepressants, and is associated with higher relapse rates during the continuation phase (5,32-33). Among the executive functions disturbed in LLD, decreased processing speed has been called "the core cognitive deficit (8,34)." Processing speed mediates performance on measures of verbal reasoning, fluency, and knowledge (35), and measures of working memory primarily depend upon speed of processing (36). Decreased processing speed has been repeatedly found in patients with LLD relative to healthy controls (8) and mediates the effects of depression and ED on daily functioning (7). The development of decreased processing speed places older individuals on a trajectory of poor outcomes, including increased risk of dementia (37), dependence in activities of daily living (ADL) (38), and driving cessation (39).

Less well recognized is the fact that depressed older adults also experience motor performance deficits, including problems with coordination (14), slowed movement (15), and difficulties with balance and gait (16). Depressive symptoms lead to the development of decreased gait speed, and slowed gait speed leads to incident depression in older adults (12-13). Decreased gait speed has been associated with a greater risk of falls (40-42), disability (14), admission to the hospital (16,43), and all-cause as well as cardiovascular mortality (44-45). While LLD and decreased gait speed are each independent risk factors for adverse health outcomes, their comorbidity synergistically increases mortality risk in older adults (46). For these reasons gait speed has become a fifth "vital sign" to be monitored in older adults, and it merits increased attention by mental health specialists treating LLD.

Post-mortem experiments and in vivo neuroimaging studies have shown that aging is associated with reduced dopamine levels, decreased D1/D2 receptor density, and loss of dopamine transporters (DAT) (17-21). Mesolimbic dopaminergic tone modulates processing speed in both humans and animal models (47), and decreased striatal dopamine transmission has been associated with decreased motor speed (48),

deterioration in frontal functioning (23), and impaired balance (49). Cham et al (2008) examined gait speed and dopamine metabolism in healthy adults aged 21-85 years, finding that lower striatal DAT activity was associated with decreased gait speed and explained 23% of the variance in gait after controlling for other factors (50). These age-associated declines in dopaminergic functioning are topographically distinct from the denervation pattern typical of Parkinson's disease (PD), being observed diffusely across the striatum rather than predominantly posterior putaminal in location (51-3). While subtle Parkinsonian-like phenomena may be observed with normal aging, the non-specific slowing associated with aging is clinically distinct from the signs and symptoms of PD. Thus, the hypodopaminergic state associated with aging and LLD has a distinct neurobiology from PD and appears to represent a parallel pathway to developing cognitive and motor deficits.

Pharmacologic augmentation of dopaminergic neurotransmission may ameliorate slowing and treat LLD. Studies in non-human primates as well as older adults with and without PD suggest that dopamine receptor agonism improves working memory (54), verbal fluency (55), problem-solving (56), and motor performance related to ADLs (57). Since slowed processing speed and gait predict the development of LLD and mediate a large portion of the disability associated with LLD, it is reasonable to hypothesize that improving slowing will positively impact LLD. Multiple case series from the 1960s onward report improved depressive symptoms (particularly psychomotor retardation) with levodopa (hereafter referred to as L-DOPA) monotherapy or augmentation (58-61). L-DOPA is the immediate precursor of dopamine, is converted to dopamine in presynaptic dopaminergic nerve terminals, and enhances dopaminergic transmission in multiple brain regions. L-DOPA has been reported to relieve depressive symptoms in new onset PD, improving symptoms in 90.3% of patients (N=31) and resulting in a mean Hamilton Rating Scale for Depression (HRSD) decrease of 11.7 points in one study (62). Relatedly, augmentation with methylphenidate, which also increases synaptic dopamine levels, was recently shown to accelerate and enhance antidepressant response in depressed older adults (63).

Despite these promising results, negative studies of L-DOPA, stimulants, and dopamine agonists as monotherapies and augmentation agents for depression also have been reported (64). One reason for these heterogeneous results is the different diagnostic criteria and experimental methodology used in older studies, which makes their results difficult to interpret. More importantly, no study examining dopamine augmentation as a treatment for depression selected subjects based upon the presence of decreased processing and gait speed. If the mechanism by which enhancing synaptic dopamine relieves depressive symptoms is by improving slowing, then including patients without slowing may contribute to negative results. By focusing on the subgroup of patients with LLD and slowing, we believe it will be possible to more clearly demonstrate the efficacy of dopaminergic agents and contribute to the development of personalized medicine for LLD.

Three types of interventions may be considered to enhance dopaminergic function and ameliorate slowing: dopamine receptor agonists (e.g., piribedil, pramipexole, ropinirole), stimulants (methylphenidate and amphetamine derivatives), and dopamine precursors such as L-DOPA. Among these options, L-DOPA enhances dopaminergic neurotransmission globally, including increasing vesicular storage, enhancing release, and stimulating post-synaptic receptors. In contrast, stimulants may not increase synaptic dopamine in individuals with diminished vesicular storage, and dopamine agonists may have reduced effects in older patients having fewer post-synaptic receptors. Moreover, a large literature shows beneficial effects of LDOPA on cognitive performance and gait in patients with PD (65-67), whereas the few available studies in

elderly patients show minimal effects of dopamine agonists (68-70) or stimulants (71) on cognition. LDOPA, especially at lower doses, is a safe and well-tolerated medication that is difficult to differentiate from placebo in terms of side effects (72). In contrast, a black box warning for adverse cardiac effects exists for stimulants, and even modest elevations in heart rate and blood pressure may significantly increase cardiac work in older patients. Similarly, dopamine agonists are associated with sleep attacks and increased impulsive behavior. For these reasons, this proposal focuses on L-DOPA as the safest, most promising pharmacologic agent for the treatment of slowing and LLD.

This study will elucidate the neurobiology of slowing and LLD, identify a novel therapeutic target for depression, and contribute to the development of personalized treatment regimens for LLD. The multimodal neuroimaging methods detailed in this application will provide information about the neurobiology of aging-associated slowing and LLD at molecular, structural, and functional levels of analysis. These data will fill a crucial gap in our knowledge regarding what are the physiologic and functional consequences of dopamine depletion occurring across the lifespan in individuals without PD. Results from this project also will allow us to evaluate a novel therapeutic approach to LLD, which could have large public health ramifications given the prevalence, frequent treatment resistance, and chronicity characteristic of LLD. Even apart from patients with LLD, cognitive and motor slowing exact a large public health burden in terms of impaired functioning and increased morbidity and mortality, and this burden will only grow as the population ages. It is critical to develop treatments capable of altering the negative health trajectories associated with slowing in order to help older adults maintain independent functioning and live longer with an increased quality of life. Finally, while PET and MRI may prove critical to understand the neurobiology of slowing and LLD, their invasiveness and expense limit their roles in informing treatment decisions in clinical practice settings. For this reason we are also assessing the influence of genetic moderators such as interleukin-6 (IL-6) and catechol-O-methyl-transferase (COMT) genotype on baseline dopamine functioning and response to L-DOPA. This may facilitate the identification of both high-risk individuals and those most likely to benefit from treatment interventions.

## Specific Aims and Hypotheses

### Specific Aims and Hypotheses

We hypothesize that treatment with levodopa (L-DOPA) will improve depressive symptoms in LLD by enhancing striatal dopamine release and improving cognitive/motor slowing. In the R33 Phase, 90 adults aged > 60 years with (1) a DSM 5 depressive disorder, (2) significant depressive symptoms (CES-D > 10), and (3) decreased processing speed (0.5 SD below age-adjusted norms on the Digit Symbol Test or Trails A) or decreased gait speed (average walking speed over 15' course < 1m/s) will be receive 8 weeks of treatment with LDOPA 450mg. Subjects will be tested for engagement of molecular target by determining whether subacute (8 week) treatment with L-DOPA displaces [C]-raclopride on positron emission tomography (PET).

R33 Phase.

Aim 1: To determine whether L-DOPA improves depressive symptoms in older adults.

Hypothesis 1: Compared to placebo, L-DOPA administration will result in greater improvements in depressive symptoms (as measured by HRSD scores).

Hypothesis 2: Greater post-L-DOPA decreases in [C]-raclopride BP and increases in processing/gait speed will be associated with greater depressive symptom improvement.

Exploratory aims: To explore the role of inflammatory markers and Catechol-O-methyl-transferase (COMT) genotype in moderating L-DOPA induced changes in slowing and depressive symptoms.

## Description of Subject Population

### Sample #1

Specify subject population

adults aged >59 years with a depressive disorder, decreased processing speed, or decreased gait speed

Number of completers required to accomplish study aims

68

Projected number of subjects who will be enrolled to obtain required number of completers

90

Age range of subject population

60 years or older

Gender, Racial and Ethnic Breakdown

On the basis of previous depression studies conducted in the Adult and Late Life Depression Research Clinic, it is anticipated that the sample will be composed of 60% women and 40% men as well as approximately 75% Caucasian, 15% African American, and 10% Hispanic subjects.

On the basis of previous depression studies conducted in the Adult and Late Life Depression Research Clinic, it is anticipated that the sample will be composed of 60% women and 40% men.

Description of subject population

This phase will enroll 90 outpatients who (1) are aged  $\geq 60$  years, (2) diagnosed with Diagnostic and Statistical Manual (DSM) 5 (107) MDD, Dysthymia, or Depression Not Otherwise Specified (NOS), (3) have Center for Epidemiologic Studies-Depression Rating scale (CES-D) (108) score  $\geq 10$ , (4) have decreased gait speed (defined as average walking speed over 15' course  $< 1\text{m/s}$ ) or decreased processing speed (defined as 1 SD below age-adjusted norms on the Digit Symbol Test), and (5) are willing to and capable of providing informed consent and complying with study procedures.

Exclusion criteria are (1) diagnosis of substance abuse or dependence (excluding Tobacco Use Disorder) within the past 12 months, (2) history of psychosis, psychotic disorder, mania, or bipolar disorder, (3) diagnosis of probable Alzheimer's Disease, Vascular Dementia, or PD, (4) Mini Mental Status Examination (MMSE)  $\leq 24$  (109), (5) HRSD suicide item  $> 2$  or Clinical Global Impressions (CGI)-Severity (110) score

of 7 at baseline, (6) current or recent (within the past 4 weeks) treatment with antidepressants, antipsychotics, or mood stabilizers, (7) history of allergy, hypersensitivity reaction, or severe intolerance to L-DOPA, (8) any physical or intellectual disability adversely affecting ability to complete assessments, (9) acute, severe, or unstable medical or neurological illness, (10) mobility limiting osteoarthritis of any lower extremity joints, symptomatic lumbar spine disease, mobility limiting history of joint replacement surgery, or history of spine surgery, (11) having contraindication to MRI scanning (such as metal in body) or unable to tolerate the scanning procedures, (12) history of significant radioactivity exposure (nuclear medicine studies or occupational exposure), and (13) presence of a clinically significant brain abnormality.

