Statistical Analysis Plan

Targeting Dopaminergic Mechanisms of Slowing to Improve Late-Life Depression

IRB #7733

NCT #03761030

Date: 07/24/15

Overview: All variables at all time points will be examined for illegitimate values, outliers, and inconsistencies. The distribution of demographic variables and baseline clinical characteristics will be examined and described across the two randomized patient groups (N=45 each) in terms of means, standard deviations, proportions, and 95% confidence intervals. Indications of inequality between groups in specific features (despite randomization) will trigger examination of whether differences in primary outcome measures can be attributed to an imbalance in group assignment. Intent-to-treat will be used for analyses including all participants who are randomized and have at least one post-baseline HRSD score. Tests will be two-sided and statistical significance determined at p-value < 0.05.

Missing data: We will make every effort to obtain all data. The longitudinal mixed modeling described below is valid if missing data are missing at random (MAR). MAR assumptions cannot be verified. A 2010 national expert panel (166) recommended sensitivity analyses for the impact of missing data via pattern mixture models (167), which we will conduct (e.g., by investigating robustness of results to perturbations of assumed values for missing data within clinically plausible ranges).

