Analyses for Aim 3: Aim 3.1: To determine whether L-DOPA administration results in greater improvements in depressive symptoms on the HRSD, a longitudinal mixed effects model will be used to analyze group differences using SAS Proc Mixed Version 9.3. The change in 24-item HRSD from baseline will be analyzed as a function of time, treatment group, the interaction between time and treatment, and baseline HRSD. Contrasts of mean difference in HRSD at each week will be formed and tested. Aim 3.2: To determine whether greater increases in processing and gait speed are associated with greater HRSD improvement, change scores from baseline to 8 weeks will be calculated for both processing and gait speed. Pearson correlation among all change scores, including change in HRSD will be examined, and two-sample t-tests will be used to assess treatment group differences. Multivariate linear regression models will be fit with change in HRSD as the outcome predicted by treatment, processing and gait speed change scores, and baseline values of processing and gait speed.

Exploratory aims: Inflammatory markers and COMT genotype will be tested as moderators of the L-DOPA effect on HRSD change by including their interactions with treatment in the Aim 3 analyses.

Power analysis: Aim 3.1: With N=45 per treatment group, and assuming a drop out of 15%, using two-sided test with $\alpha=0.05$, we have >80% power to detect treatment group differences with ES = 0.60 or greater. Given expected SD=5 points based on similar previously conducted studies in the LLDRRC, this ES would correspond to a change in HRSD of 3 points, which is smaller than the 4 point change considered meaningful. Aim 3.2: With N=90, assuming a drop out of 15%, we would be able to detect correlations >0.31. Thus, we have adequate power to detect a moderate to large correlations between change in HRSD and change in processing and gait speed.

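### The protocol's 68 completers from 90 enrolled implies about 24% loss, the SAP assumes 15%, and 68 completers do not support the SAP's detectable effects

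*Protocol*

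**What the plan says.** **Protocol, Description of Subject Population, Sample #1.** The entry for "Number of completers required to accomplish study aims" is 68. The entry for "Projected number of subjects who will be enrolled to obtain required number of completers" is 90. The same section repeats the enrolment: "This phase will enroll 90 outpatients who" meet the listed criteria. It gives no dropout rate.

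**SAP, Overview.** The 90 are the randomized patients: "two randomized patient groups (N=45 each"). On testing: "Tests will be two-sided and statistical significance determined at p-value < 0.05". The analysis set is anyone randomized who has an HRSD rating after baseline, so it is not limited to completers.

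**SAP, Power analysis.** For Aim 3.1: "With N=45 per treatment group, and assuming a drop out of 15" per cent, "we have >80% power to detect treatment group differences with ES = 0.60 or greater". With SD 5 this is put at 3 HRSD points, against 4 points regarded as meaningful. For Aim 3.2: "With N=90, assuming a drop out of 15%, we would be able to detect correlations >0.31". The SAP states no number of completers.

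**The concern.** The protocol's second entry presents 90 as the enrolment needed to reach 68, so it carries an attrition assumption even though no rate is printed. The SAP prints a different rate for the same 90 patients. The expected number of completers differs by 8 to 9, too many for rounding.

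What is at stake is the meaning of the word required. If the aims need 68 completers, then 68 should deliver the sensitivity that the SAP claims for them. If it does not, a trial that finishes with 68 satisfies the protocol's entry while being less sensitive than the SAP says.

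**Working it through.** **Inputs.** 68 completers and 90 enrolled (Protocol, Sample #1); 45 per arm, two-sided 0.05 (SAP, Overview); 15% dropout, ES 0.60, SD 5, more than 80% power, r > 0.31 (SAP, Power analysis). Assumptions made here: losses split equally between arms, and 80% power for the correlation, because the SAP gives no power for Aim 3.2.

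**Step 1: attrition.**
- Loss implied by the protocol: 1 − 68/90 = 22/90 = 24.4%.
- Completers implied by the SAP: 90 × 0.85 = 76.5, or 38.25 per arm.
- Enrolment needed for 68 at 15% loss: 68/0.85 = 80, not 90.
- The pair 68 and 90 fits about 25% loss (90 × 0.75 = 67.5), a rate that appears in neither document.

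**Step 2: Aim 3.1 as a plain two-sample t comparison.** Noncentrality is ES × √(n/2) with n per arm, on 2n − 2 degrees of freedom. For ES 0.60 it is 0.60 × √22.5 = 2.85 at 45 per arm, 0.60 × √19 = 2.62 at 38, and 0.60 × √17 = 2.47 at 34.

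| | 45 per arm (no loss) | 38 per arm (15% loss) | 34 per arm (68 completers) |
|---|---|---|---|
| Power at ES 0.60 | 80.4% | 73.3% | 68.4% |
| ES for 80% power | just under 0.60 | 0.65 | 0.69 |
| In HRSD points, SD 5 | about 3.0 | about 3.25 | 3.45 |
| Power at 4 points (ES 0.80) | 96% | 93% | 90% |

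In this comparison the SAP's ES 0.60 at more than 80% power is reproduced only with the full 45 per arm. It is not reproduced at 15% loss, and still less at 68 completers.

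**Step 3: what baseline adjustment could add.** The SAP's model includes baseline HRSD. If SD 5 is the unadjusted SD, adjustment multiplies it by √(1 − ρ²), where ρ is the baseline–outcome correlation. The documents give no ρ. By normal approximation, for ρ from 0 to 0.6, power at ES 0.60 runs from 74% to 90% at 38 per arm and from 70% to 87% at 34. Reaching 80% needs ρ of about 0.36 and 0.47 respectively.

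**Step 4: Aim 3.2 by Fisher's z.** Detectable r = tanh[(1.960 + 0.842)/√(n − 3)].

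| n | Detectable r, 80% power | Power at r = 0.31 |
|---|---|---|
| 77 | 0.315 | 78.7% |
| 76 | 0.317 | 78.2% |
| 68 | tanh(2.802/√65) = 0.334 | 73.4% |

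The SAP's 0.31 is close to the value at 15% loss. It does not fit 68 completers.

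**The case against.** **68 is a minimum.** A 15% loss from 90 leaves 76 or 77, which is more than 68. A reader might infer that the two documents cannot both hold. That goes too far: a trial can need 68, enrol 90 and expect to lose 15%. What stands is narrower. The protocol labels 90 as the number needed to obtain 68, not as 68 plus a margin, and no margin is explained.

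**Enrolled is not randomized.** In the protocol's Study Procedures, consent comes before the rest of the baseline work, and randomization is at Week 0. Loss before randomization could therefore account for the extra attrition. It cannot here, because the SAP also counts 90 as randomized, 45 per arm. The protocol does not define a completer, however.

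**The primary analysis is not a completer analysis.** This is correct. HRSD is rated weekly, the mixed model uses partial data from patients who leave, and it adjusts for baseline HRSD. The Aim 3.1 figures above are therefore conservative. The defence does not carry over to Aim 3.2, which uses changes from baseline to week 8. A patient without week-8 values has no change score to contribute.

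**Not all SAP figures rest on 76–77.** A reader might infer that every detectable effect in the SAP assumes that number. Only the correlation roughly does. ES 0.60 matches the full 45 per arm in a plain comparison, so adopting 15% throughout would not by itself restore the stated power.

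**The effect is small.** Moving from 15% to 24% loss shifts the detectable difference from about 3.25 to 3.45 points and r from about 0.316 to 0.334. Both differences are below 4 points, and 34 per arm has about 90% power for 4 points. This limits the seriousness of the point but does not reconcile the figures.

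**Conclusion.** The concern holds as an inconsistency between two planning assumptions: about 24% loss implied by the protocol and 15% stated in the SAP, a gap of 8 to 9 completers with no reconciliation. The number the protocol calls required does not support the SAP's stated sensitivity. At 68 completers, a plain two-sided comparison has about 68% power at ES 0.60 and needs ES 0.69 for 80%. The Aim 3.2 correlation detectable with 80% power is about 0.33.

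These values assume equal loss by arm, SD 5, and for Aim 3.1 no gain from baseline adjustment or partial data. The figure of 76–77 is derived from 90 and 15%; the SAP does not print it.

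The documents do not support reading this as a trial that is too small for its own meaningful difference. They also do not support putting 76 in place of 68 as the required number: 76 is an expected yield, and no calculation in either document makes it a requirement. The point should be corrected, but it does not threaten the design.

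**What to change.** Keep enrolment at 90. Choose one attrition assumption, use it in both documents, and restate the detectable values to match:

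- **About 24% loss (68 completers).** Keep 68 in the protocol. In both SAP power statements replace 15% with 24%, and give ES 0.69 (3.45 points at SD 5) and r about 0.33.
- **15% loss (76–77 completers).** Keep 15% in the SAP and give ES about 0.65 (about 3.25 points) and r about 0.315. In the protocol, give 76–77 as the expected number of completers, and either justify 68 as the required number or remove it.

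In either case, say what counts as a completer. If the sponsor wishes to claim credit for baseline adjustment or partial data in Aim 3.1, state the assumed baseline–outcome correlation and show the calculation.

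The cost is wording only. No patients, visits or analyses are added. The stated detectable effects become slightly less favourable under either choice, and the detectable HRSD difference stays below 4 points.
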